10 ADMINISTRATIVE REQUIREMENTS

10.1 Product Complaints

A product complaint is a verbal, written, or electronic expression that implies dissatisfaction regarding the identity, strength, purity, quality, or stability of a drug product. Individuals who identify a potential product complaint situation should immediately contact MedComm Solutions (see below) and report the event. Whenever possible, the associated product should be maintained in accordance with the label instructions pending further guidance from a Millennium Quality representative.

For Product Complaints,

- Phone: [name] ([name])
- E-mail: [contact]
- [contact]
- Hours: Mon-Fri, 8 a.m. – 6 p.m. ET

Product complaints in and of themselves are not AEs. If a product complaint results in an SAE, an SAE form should be completed and sent to Millennium Pharmacovigilance (refer to Section 9.2).

10.2 Compliance with Protocol and Protocol Revisions

The study must be conducted as described in this approved protocol. All requests for revisions to the protocol must be provided to ERP. The Investigator should not implement any deviation or change to the protocol without prior review and documented approval/favorable opinion from the IRB/IEC of an Amendment, except where necessary to eliminate an immediate hazard(s) to study patients. Documentation of approval signed by the chairperson or designee of the IRB(s)/IEC(s) must be sent to the ERP. If the revision is an Administrative Letter, Investigators must inform their IRB(s)/IEC(s). ERP will work with Fox Chase Cancer Center Coordinating Center to ensure they are in receipt of all required documents.

10.3 Data Collection

An Investigator is required to prepare and maintain adequate and accurate case histories designed to record all observations and other data pertinent to the investigation on each individual treated with the investigational product.

10.4 Institutional Review Board/Independent Ethics Committee (IRB/IEC)

Before study initiation, the Investigator must have written and dated approval/favorable opinion from the IRB/IEC for the protocol, consent form, patient recruitment materials/process (e.g., advertisements), and any other written information to be provided to patients. The Investigator should also provide the IRB/IEC with a copy of the product labeling, information to be provided to patients, and any updates.

The Investigator should provide the IRB/IEC with reports, updates, and other information (e.g., Safety Updates, Amendments, and Administrative Letters) according to regulatory requirements or Institution procedures. Copies of the initial IRB approval as well as annual re-approvals must be submitted to ERP.

10.5 Records Retention

The Investigator must retain investigational product disposition records and source documents for the maximum period required by applicable regulations and guidelines, or Institution procedures. If the Investigator withdraws from the study (e.g., relocation, retirement), the records shall be transferred to a mutually agreed upon designee (e.g., another Investigator, IRB). Notice of such transfer will be given in writing to ERP.

12 APPENDICES

12.1 Eastern Cooperative Oncology Group (ECOG) Scale for Performance Status

Grade	Description
0	Normal activity. Fully active, able to carry on all predisease performance without restriction
1	Symptoms but ambulatory. Restricted in physically strenuous activity, but ambulatory and able to carry out work of a light or sedentary nature (eg, light housework, office work)
2	In bed < 50% of the time. Ambulatory and capable of all self-care, but unable to carry out any work activities. Up and about more than 50% of waking hours.
3	In bed > 50% of the time. Capable of only limited self-care, confined to bed or chair more than 50% of waking hours.
4	100% bedridden. Completely disabled. Cannot carry on any self-care. Totally confined to bed or chair
5	Dead

Source: Oken MM, Creech RH, Tormey DC, Horton J, Davis TE, McFadden ET et al. Toxicity and response criteria of the Eastern Cooperative Oncology Group. Am J Clin Oncol 1982; 5 (6):649-55.

12.2 Cockcroft-Gault Equation

For males:

$$\text{Creatinine Clearance} = \frac{(140 - \text{age}[years] \times \text{weight [kg]})}{72 \times (\text{serum creatinine[mg/dL]})} \quad \text{OR} \quad \frac{(140 - \text{age}[years] \times \text{weight [kg]})}{0.81 \times (\text{serum creatinine}[\mu\text{mol/L}])}$$

For females:

$$\text{Creatinine Clearance} = \frac{0.85 (140 - \text{age}[years] \times \text{weight [kg]})}{72 \times (\text{serum creatinine[mg/dL]})} \quad \text{OR} \quad \frac{0.85 (140 - \text{age}[years] \times \text{weight [kg]})}{0.81 \times (\text{serum creatinine}[\mu\text{mol/L}])}$$

Source: Cockcroft DW, Gault MH. Prediction of creatinine clearance from serum creatinine. *Nephron* 1976;16(1):31-41.

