5. STUDY POPULATION

5.1 Inclusion Criteria

Each patient must meet all of the following inclusion criteria to be enrolled in the study:

1. Male or female patients 18 years or older.
2. Voluntary written consent must be given before performance of any study related procedure not part of standard medical care, with the understanding that consent may be withdrawn by the patient at any time without prejudice to future medical care.
3. Female patients must be:
 - Postmenopausal for at least 1 year before the screening visit, OR
 - Surgically sterile, OR
 - If they are of childbearing potential, agree to practice 2 effective methods of contraception, at the same time, from the time of signing the informed consent form through 90 days after the last dose of study drug, OR
 - Agree to practice true abstinence when this is in line with the preferred and usual lifestyle of the subject. (Periodic abstinence [eg, calendar, ovulation, symptothermal, post-ovulation methods] and withdrawal are not acceptable methods of contraception.)
4. Male patients, even if surgically sterilized (ie, status post-vasectomy), must agree to practice effective barrier contraception during the entire study treatment period and through 90 days after the last dose of study drug, or agree to practice true abstinence when this is in line with the preferred and usual lifestyle of the subject. (Periodic abstinence [eg, calendar, ovulation, symptothermal, post-ovulation methods] and withdrawal are not acceptable methods of contraception.)
5. Patients must have a diagnosis of a metastatic renal cell carcinoma with a $\geq 50\%$ clear cell component.
6. Eastern Cooperative Oncology Group (ECOG) performance status 0, 1, or 2.
7. Patients must meet the following clinical laboratory criteria:
 - Absolute neutrophil count (ANC) $\geq 1,000/\text{mm}^3$ and platelet count $\geq 100,000/\text{mm}^3$ and hemoglobin $\geq 9 \text{ g/dL}$. Platelet or red cell transfusions to help patients meet eligibility criteria are not allowed within 3 days before study enrollment.
 - Total bilirubin $\leq 1.5 \times$ the upper limit of the normal range (ULN).

- Alanine aminotransferase (ALT) and aspartate aminotransferase (AST) $\leq 3 \times$ ULN.
- Calculated by Cockcroft-Gault or measured by 24 hour urine creatinine clearance ≥ 50 mL/min (see Section 12.2).

8. Measurable disease by RECIST 1.1.
9. Receipt of at least two line of prior therapy for metastatic RCC.

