Pegylated IFN- α -2b Administration

Pegylated IFN- α -2b (PegIntron): Each patient will be treated with Pegylated IFN- α -2b by subcutaneous injection in clinic by a registered nurse or at home by self-injection after proper training. They will write down in a patient diary the time of administration and dose

if they are injecting at home. The dose will be based on phase of study (see section 4-1). The drug will be obtained commercially in various vial strengths depending on patient's weight in kg (see below). The injection site will be rotated between thigh, outer surface of upper arm, and abdomen. Injections will not be given near navel or waistline; patients who are thin will only have thigh or upper arm used. No injection will be given into a bruised, infected, irritated, red, or scarred skin.

All patients will be pre-medicated with acetaminophen (500-1000 mg orally) 30 minutes prior to the first dose and as needed for subsequent doses thereafter.

Dose in mL=Weight (kg) x Dose (μ g/kg)/Reconstituted Vial Strength (μ g/mL)

For patients whose CrCl was acceptable for study eligibility/entry per a 24 hour urine creatinine clearance, but not Cockcroft-Gault, if serum creatinine increases by 20% or more, the dose of pegylated IFN will be reduced by 25% for the particular dose level the patient is at and not re-escalated.

If a patient's CrCl was acceptable per Cockcroft-Gault for study eligibility/entry, if CrCl drops to between 30-50 ml/min while on treatment, the dose of pegylated IFN will be reduced by 25% for the particular dose level the patient is at and not re-escalated.

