If not recovered to \leq Grade 1 or baseline within 4 weeks	
 Reduce IFN to next lower dose upon return to \leq Grade 1 or baseline 	Monitor closely, take appropriate medical precautions, and provide appropriate symptomatic care
Subsequent recurrence Grade 3 that does not recover to \leq Grade 1 or baseline within 4 weeks	
 Hold IFN until resolution to Grade ≤ 1 or baseline Reduce IFN to next lower dose 	Monitor closely, take appropriate medical precautions, and provide appropriate symptomatic care
Grade 4 non-hematologic toxicities judged to be related to study drug	Consider permanently discontinuing study drug	Exceptions may be made in cases in which the investigator determines the patient is obtaining a clinical benefit

Renal Impairment Dose Adjustment:

For patients whose CrCl was acceptable for study eligibility/entry per a 24 hour urine creatinine clearance, but not Cockcroft-Gault, if serum creatinine increases by 20% or more, the dose of pegylated IFN will be reduced by 25% for the particular dose level the patient is at and not re-escalated.

If a patient's CrCl was acceptable per Cockcroft-Gault for study eligibility/entry, then if CrCl drops to between 30-50 ml/min while on treatment, the dose of pegylated IFN will be reduced by 25% for the particular dose level the patient is at and not re-escalated.

Once Ixazomib or pIFN is reduced for any toxicity, the dose may not be re-escalated.

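### Appendix 12.2 closes the Cockcroft-Gault bracket after weight in all four expressions, so the printed clearance is negative for every adult (minor correction)

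*Combined protocol and SAP*

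**What the plan says.** Appendix 12.2 gives four expressions for creatinine clearance: males and females, each with serum creatinine in mg/dL or in µmol/L.

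- The male numerator is "140 - \text{age}[years] \times \text{weight [kg" in both unit versions. The bracket opens before 140 and closes after weight.
- The female numerator is "0.85 (140 - \text{age}[years] \times \text{weight [kg", with the same bracket placement.
- The denominators are "72 \times (\text{serum creatinine[mg/dL" and "0.81 \times (\text{serum creatinine}[\mu\text{mol/L".
- The publication that introduced the equation is cited directly below.

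Three other places use clearance.

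- Section 5.1, criterion 7, sets the limit of 50 mL/min, "Calculated by Cockcroft-Gault or measured by 24 hour urine creatinine clearance", and refers to Section 12.2.
- Section 6.2 lowers the pIFN dose by 25%, without later re-escalation, in patients who entered by Cockcroft-Gault, "if CrCl drops to between 30-50 ml/min while on treatment". The renal adjustment text after Table 6-3 in Section 6.4 repeats this rule.
- Patients who qualified on the 24-hour urine value but not on Cockcroft-Gault have a separate rule in both sections: "if serum creatinine increases by 20% or more, the dose of pegylated IFN will be reduced by 25" percent.

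No other section prints the equation.

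**The concern.** An appendix cited by an eligibility criterion should give a number that can be used against that criterion. With the bracket after weight, multiplication comes before subtraction and the numerator is 140 - (age × weight). The result is negative for any adult and moves the wrong way: as creatinine rises, the value climbs towards zero when clearance should fall.

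If the text were followed literally, nobody could qualify on the calculated route, because a negative value is always below 50. Nor could a recalculated clearance ever fall between 30 and 50 mL/min, so the dose reduction for patients who entered by Cockcroft-Gault would never be triggered. The protocol gives a pharmacological reason for caring about this range: its pIFN background section reports that drug clearance is roughly halved when creatinine clearance is below 50 mL/min.

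**Working it through.** The plan states no worked clearance value, so there is no figure to reproduce. Each expression is evaluated as printed and then with the bracket closed after age.

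**Inputs from the protocol.** Sex factor f = 1 (male) or 0.85 (female); k = 72 (mg/dL) or 0.81 (µmol/L), from Appendix 12.2. Minimum age 18 and the 50 mL/min limit, from Section 5.1. The 30-50 mL/min band, from Sections 6.2 and 6.4.

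**Assumptions, not in the protocol.** The patients' age, weight and creatinine (Scr). For the µmol/L forms, 106 µmol/L is taken as the counterpart of 1.2 mg/dL (1.2 × 88.4 = 106.1).

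**Formulas.**

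- As printed: f × (140 - age × weight) / (k × Scr)
- Regrouped: f × (140 - age) × weight / (k × Scr)

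**Sign.** The printed numerator is negative when age × weight exceeds 140. At age 18 that means any weight above 140 / 18 = 7.8 kg, and the cut-off is lower at older ages.

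**Examples (mL/min).**

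| Patient | Scr | As printed | Regrouped |
|---|---|---|---|
| Male, 60 y, 80 kg | 1.2 mg/dL | (140 - 4800) / 86.4 = -53.9 | 80 × 80 / 86.4 = 74.1 |
| Male, 60 y, 80 kg | 106 µmol/L | -4660 / 85.86 = -54.3 | 6400 / 85.86 = 74.5 |
| Female, 70 y, 60 kg | 1.2 mg/dL | 0.85 × (140 - 4200) / 86.4 = -39.9 | 0.85 × 70 × 60 / 86.4 = 41.3 |
| Female, 70 y, 60 kg | 106 µmol/L | 0.85 × (-4060) / 85.86 = -40.2 | 0.85 × 4200 / 85.86 = 41.6 |

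The two unit versions agree closely once regrouped, which suggests that the denominators are sound and only the numerator needs changing.

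**Direction.** For the same man, let creatinine rise from 1.2 to 1.8 mg/dL. The printed value goes up, from -53.9 to -4660 / 129.6 = -36.0. The regrouped value goes down, from 74.1 to 6400 / 129.6 = 49.4, which enters the band for dose reduction.

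**Range.** Over ages 18-90, weights 35-160 kg and creatinine 0.4-4.0 mg/dL, the male mg/dL form as printed is never zero or positive. Its largest value is at 18 years, 35 kg and 4.0 mg/dL: (140 - 630) / 288 = -1.7.

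**Intended grouping.** The three numerator terms, in their printed order, can be grouped in two ways only. Only (140 - age) × weight gives positive values that fall as creatinine rises, so the protocol's own thresholds settle the correction.

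**The case against.** The strongest objection is provenance. The formula was typeset and then converted by a program, and a misplaced bracket is the kind of damage conversion can cause. The four numerators are nearly the same string, so a converter that misread one could misread all four; they are not four independent observations. This stands as a reason to check the source PDF first. It does not remove the point. The brackets are balanced and identically placed in all four expressions and the denominator brackets are intact, which makes a misprint in the source the likelier explanation.

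The second objection is materiality, and most of it stands. The equation is named wherever it is used and its source is cited, so a clinician would almost certainly apply the standard form. A negative clearance would be noticed at the first patient. A measured 24-hour clearance is an accepted route to entry, with its own dose rule.

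Third, only criterion 7 refers to Appendix 12.2. Sections 6.2 and 6.4 name the method without citing the appendix, so the dosing rule depends on the printed expression less directly than the entry criterion does. That is fair, although the appendix is the only statement of the method in the protocol.

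**Conclusion.** The point holds as a minor correction to operative text. As extracted, all four expressions give a negative clearance for every adult, for example -53.9 in place of 74.1 mL/min, and cannot serve the 50 mL/min limit or the 30-50 mL/min band. The sign result needs only the minimum age of 18 and a weight above 7.8 kg; the individual examples rest on assumed patient values. Confidence is medium because the source PDF has not been seen.

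Actual misclassification of patients is unlikely. This is not a failure of the eligibility rule or of the renal safeguard, and no threshold, endpoint, sample size or operating characteristic changes.

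**What to change.** 1. Compare the bracket in Appendix 12.2 with the source PDF.
2. If it is as extracted, change the numerator in all four expressions to (140 - age [years]) × weight [kg]. Keep the 0.85 factor for females and both denominators.
3. Confirm that any eligibility worksheet or calculator in use applies that grouping. The protocol does not say whether one exists.

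The cost is one bracket moved in four expressions, which can go into the next amendment, plus a short check of any tool in use.

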12.3 Statistical Considerations and Operating Characteristics for Phase II

Operating characteristics of the design depend on four conditions: toxicity being low (0.05) or high (0.25) and PFS at 16 weeks being low (0.35) or high (0.56). They are summarized below:

1. Toxicity = 0.05 and PFS = 0.56. In this case the power of the study is at least 80%. The chance of early stopping (in error) for excess toxicity is less than 1%. The chance for stopping (in error) for futility varies from 8% to 12% depending on the relation of toxicity to PFS (see details below).
2. Toxicity = 0.05, PFS = 0.35. The chance of early stopping for futility varies from 49% to 57%. The chance of declaring treatment efficacious (type I error) varies from 10% to 21%.
3. Toxicity = 0.25 and PFS = 0.35. Type I error varies from less than 1% to about 5%. Chance of stopping early for either excess toxicity or futility varies from about 26% to about 59%.
4. Toxicity = 0.25 and PFS = 0.56. Type I error varies from about 5% to about 10%. Chance of early stopping for excess toxicity is about 27%.

The term 'UT' here means severe toxicity for which, if frequent enough, dictates dose reduction or trial termination. This early stopping design is an extension of the method of Litwin, Wong and Hudes (Statistics in Medicine, 2007,26:4400-4415). Below, the chance that a patient has a UT and also is PF at 16 weeks is represented by 'a'. 'b', 'c' and 'd', similarly, represent the indicated joint probabilities.

Let $p = p(\text{PFS} > 16 \text{ weeks})$, $p_1 = p(\text{PFS} > 8 \text{ weeks})$ and $p_2 = p(\text{PFS} > 16 \text{ weeks} | \text{PFS} > 8 \text{ weeks})$. Also, let $\text{ptox} = p(\text{UT in 16 weeks})$. Let $\text{ptox1} = f^* \text{ptox} = p(\text{UT in initial 8 week period})$ and $\text{ptox2} = (1-f)^* \text{ptox} = p(\text{UT in 8 through 16 week period} | \text{no UT in the initial 8 weeks})$. Then, $b = p - a$, $c = \text{ptox} - a$ and $d = 1 - a - b - c$. a_1, b_1, c_1 , and d_1 are similarly determined from p_1 and ptox1 . a_2, b_2, c_2 and d_2 are determined likewise, from p_2 and ptox2 .

The table:

$P(\text{UT})$	$1 - p(\text{UT})$	
a	b	$p(\text{PFS} > 16 \text{ weeks}) = 0.56$ (under the alternative hypothesis)
c	d	$p(\text{PFS} < 16 \text{ weeks}) = 0.44$
ptox	$1 - \text{ptox}$	1 ($\text{ptox} = 0.05$ under the alternative hypothesis)

Illustrates how the joint event probabilities a, b, c and d at the end of the study relate. Namely, if we assign $a = 0.02$ then b, c and d can be determined by subtraction. Here we would get: $b = 0.54$, $c = 0.03$ and $d = 0.41$. For any value of a in $(0, 0.05)$ the other three terms are completely specified. In this design we are considering toxicity to be cumulative. We model the total chance of UT to occur with fraction f in the first interval (0, 8 weeks) and $1-f$ in the final 8 weeks. We have considered fractions $f = 0, 0.25, 0.5, 0.75$ and 1.0 , i.e. $f=0$ implies no toxicity in the first 8 weeks and $f = 1$ implies all toxicity occurs then. The final design is based on $f = \frac{1}{2}$.

P(UT)	1-p(UT)
a1	b1 p(PFS > 8) = 0.66
c1	d1 p(PFS < 8) = 0.34
ptox1	1 - ptox1 1 (ptox1 = ptox2 = 0.025 under the alternative with $f = \frac{1}{2}$) and
P(UT)	1-p(UT)
a2	b2 p(PFS > 16 PFS > 8) = 0.848
c2	d2 p(PFS < 16 PFS > 8) = 0.15
ptox2	1 - ptox2 1

The two tables above characterize the early stopping interval (0, 8 weeks) and final interval (8 weeks, 16 weeks). Numbers in the tables represent the alternative hypothesis. Patients in the initial cohort are represented by the top table (a1, b1, c1, d1) in the initial interval and those who are toxicity and progression free at 8 weeks, hence continue on study are represented by the second table (a2, b2, c2, d2) for their second 8 weeks. Patients recruited into the second cohort, if the study makes it past the first 8 week period, are evaluated only at 16 weeks and are represented by the very first table (a, b, c, d).

The chance of early stopping for excess toxicity, for futility, the chance of final declaration of excess toxicity, the power or type I error were all computed for each of the 4 conditions. Within each of these combinations, the fraction, f, of toxicity born within the first 8 weeks was varied in 5 steps from 0 to 1. We selected the number $f = \frac{1}{2}$ in the belief that toxicity is cumulative and this is the maximum fraction expected to occur in the first half of the trial. Design behavior for $f < \frac{1}{2}$ is ‘better’ than that for $f > \frac{1}{2}$, so is not reported here in detail.

The table below lists the various operating probabilities as functions of ‘a’ for each of the four conditions.

Key:

null = 0: PFS at 16 weeks = 0.35

null = 1: PFS at 16 weeks = 0.56

ntox = 0: Toxicity = 0.05

ntox = 1: Toxicity = 0.25

a: probability that PFS > 16 weeks and patient had UT

tox: probability of early stopping for excess toxicity

fut: probability of early stopping for futility

toxend: probability that final decision is 'too toxic'

alpha: type I error, probability of declaring efficacy when

either PFS = 0.35 at 16 weeks or toxicity = 0.25

power: probability of declaring efficacy when PFS at 16 weeks is
0.56 and toxicity is 0.05.

null	ntox	a	tox	fut	toxend	alpha	cksum
0	0	0.00	0.0059	0.4938	0.0115	0.2116	1.0000
0	0	0.01	0.0059	0.5105	0.0111	0.1871	1.0000
0	0	0.02	0.0059	0.5271	0.0107	0.1642	1.0000
0	0	0.03	0.0059	0.5437	0.0103	0.1429	1.0000
0	0	0.04	0.0059	0.5602	0.0099	0.1233	1.0000
0	0	0.05	0.0059	0.5766	0.0095	0.1054	1.0000

null	ntox	a	tox	fut	toxend	alpha	cksum
0	1	0.00	0.2690	0.2920	0.3671	0.0493	1.0000
0	1	0.01	0.2690	0.3050	0.3561	0.0451	1.0000
0	1	0.02	0.2690	0.3181	0.3450	0.0410	1.0000
0	1	0.03	0.2690	0.3312	0.3339	0.0369	1.0000
0	1	0.04	0.2690	0.3444	0.3227	0.0329	1.0000

0	1	0.05	0.2690	0.3576	0.3115	0.0291	1.0000
0	1	0.06	0.2690	0.3708	0.3003	0.0255	1.0000
0	1	0.07	0.2690	0.3840	0.2892	0.0221	1.0000
0	1	0.08	0.2690	0.3972	0.2781	0.0189	1.0000
0	1	0.09	0.2690	0.4103	0.2671	0.0161	1.0000
0	1	0.10	0.2690	0.4233	0.2562	0.0134	1.0000
0	1	0.11	0.2690	0.4361	0.2454	0.0111	1.0000
0	1	0.12	0.2690	0.4489	0.2347	0.0091	1.0000
0	1	0.13	0.2690	0.4615	0.2241	0.0073	1.0000
0	1	0.14	0.2690	0.4739	0.2137	0.0058	1.0000
0	1	0.15	0.2690	0.4860	0.2035	0.0045	1.0000
0	1	0.16	0.2690	0.4980	0.1935	0.0035	1.0000
0	1	0.17	0.2690	0.5097	0.1837	0.0026	1.0000
0	1	0.18	0.2690	0.5212	0.1741	0.0020	1.0000
0	1	0.19	0.2690	0.5324	0.1648	0.0014	1.0000
0	1	0.20	0.2690	0.5433	0.1557	0.0010	1.0000
0	1	0.21	0.2690	0.5540	0.1468	0.0007	1.0000
0	1	0.22	0.2690	0.5643	0.1382	0.0005	1.0000
0	1	0.23	0.2690	0.5742	0.1299	0.0003	1.0000
0	1	0.24	0.2690	0.5839	0.1219	0.0002	1.0000
0	1	0.25	0.2690	0.5932	0.1141	0.0001	1.0000

null	ntox	a	tox	fut	toxend	power	cksum
1	0	0.00	0.0059	0.0817	0.0234	0.8759	1.0000
1	0	0.01	0.0059	0.0888	0.0231	0.8653	1.0000

1	0	0.02	0.0059	0.0963	0.0228	0.8535	1.0000
1	0	0.03	0.0059	0.1042	0.0225	0.8404	1.0000
1	0	0.04	0.0059	0.1125	0.0222	0.8259	1.0000
1	0	0.05	0.0059	0.1213	0.0219	0.8099	1.0000

null	ntox	a	tox	fut	toxend	alpha	cksum
1	1	0.00	0.2690	0.0247	0.6054	0.1010	1.0000
1	1	0.01	0.2690	0.0279	0.6021	0.1011	1.0000
1	1	0.02	0.2690	0.0313	0.5985	0.1012	1.0000
1	1	0.03	0.2690	0.0351	0.5947	0.1012	1.0000
1	1	0.04	0.2690	0.0391	0.5907	0.1011	1.0000
1	1	0.05	0.2690	0.0435	0.5864	0.1009	1.0000
1	1	0.06	0.2690	0.0483	0.5818	0.1006	1.0000
1	1	0.07	0.2690	0.0533	0.5770	0.1002	1.0000
1	1	0.08	0.2690	0.0587	0.5718	0.0997	1.0000
1	1	0.09	0.2690	0.0645	0.5664	0.0990	1.0000
1	1	0.10	0.2690	0.0706	0.5607	0.0981	1.0000
1	1	0.11	0.2690	0.0771	0.5548	0.0970	1.0000
1	1	0.12	0.2690	0.0840	0.5485	0.0957	1.0000
1	1	0.13	0.2690	0.0912	0.5419	0.0941	1.0000
1	1	0.14	0.2690	0.0988	0.5350	0.0923	1.0000
1	1	0.15	0.2690	0.1068	0.5278	0.0901	1.0000
1	1	0.16	0.2690	0.1152	0.5203	0.0877	1.0000
1	1	0.17	0.2690	0.1239	0.5126	0.0850	1.0000
1	1	0.18	0.2690	0.1330	0.5045	0.0819	1.0000

1	1	0.19	0.2690	0.1425	0.4962	0.0786	1.0000
1	1	0.20	0.2690	0.1522	0.4876	0.0749	1.0000
1	1	0.21	0.2690	0.1624	0.4787	0.0710	1.0000
1	1	0.22	0.2690	0.1728	0.4696	0.0668	1.0000
1	1	0.23	0.2690	0.1836	0.4602	0.0625	1.0000
1	1	0.24	0.2690	0.1947	0.4506	0.0580	1.0000
1	1	0.25	0.2690	0.2060	0.4408	0.0533	1.0000

Our analysis above is based on the assumption that toxicity is judged at 8 weeks and again at 16 weeks. In fact, the phase I portion of the study will not last beyond 4 weeks for each patient, so that the initial 3 patients, carried over from phase I, could become UT at 8 weeks. The tables above assume that the number of UTs at 8 weeks (not 4 weeks) is at most one. To account for this possibility, we re-computed the table assuming no restriction on the first 6 patients, but using only the early stopping rules for toxicity at 8 weeks. Thus the initial phase II cohort of all 17 patients in this re-computation are all treated alike. The results are shown in the next table. While the table above allows a smaller chance of toxicity than the actual trial, the table below allows a greater chance of toxicity in the initial phase II cohort. The main difference in the two computations is that the chance of early stopping for UT is about 9% higher under the re-computation conditions (35%) than it is under the top table (27%).

Operating characteristics of design with no restriction on the first 6 patients other than those tested at 8 or 16 weeks.

null	ntox	a	tox	fut	toxend	alpha	cksum
0	0	0.00	0.0082	0.4937	0.0114	0.2106	1.0000
0	0	0.01	0.0082	0.5103	0.0110	0.1862	1.0000
0	0	0.02	0.0082	0.5269	0.0106	0.1633	1.0000
0	0	0.03	0.0082	0.5434	0.0102	0.1421	1.0000
0	0	0.04	0.0082	0.5599	0.0098	0.1227	1.0000
0	0	0.05	0.0082	0.5762	0.0094	0.1049	1.0000

null	ntox	a	tox	fut	toxend	alpha	cksum
0	1	0.00	0.3591	0.2586	0.3197	0.0429	1.0000
0	1	0.01	0.3591	0.2700	0.3100	0.0393	1.0000
0	1	0.02	0.3591	0.2814	0.3003	0.0357	1.0000
0	1	0.03	0.3591	0.2929	0.2905	0.0321	1.0000
0	1	0.04	0.3591	0.3045	0.2807	0.0286	1.0000
0	1	0.05	0.3591	0.3161	0.2709	0.0253	1.0000
0	1	0.06	0.3591	0.3277	0.2612	0.0221	1.0000
0	1	0.07	0.3591	0.3392	0.2514	0.0192	1.0000
0	1	0.08	0.3591	0.3507	0.2417	0.0164	1.0000
0	1	0.09	0.3591	0.3622	0.2321	0.0139	1.0000
0	1	0.10	0.3591	0.3735	0.2225	0.0117	1.0000
0	1	0.11	0.3591	0.3848	0.2131	0.0096	1.0000
0	1	0.12	0.3591	0.3959	0.2038	0.0079	1.0000
0	1	0.13	0.3591	0.4069	0.1945	0.0063	1.0000
0	1	0.14	0.3591	0.4177	0.1855	0.0050	1.0000
0	1	0.15	0.3591	0.4283	0.1766	0.0039	1.0000
0	1	0.16	0.3591	0.4388	0.1679	0.0030	1.0000
0	1	0.17	0.3591	0.4490	0.1593	0.0023	1.0000
0	1	0.18	0.3591	0.4590	0.1510	0.0017	1.0000
0	1	0.19	0.3591	0.4688	0.1428	0.0012	1.0000
0	1	0.20	0.3591	0.4783	0.1349	0.0009	1.0000
0	1	0.21	0.3591	0.4875	0.1272	0.0006	1.0000
0	1	0.22	0.3591	0.4965	0.1197	0.0004	1.0000
0	1	0.23	0.3591	0.5051	0.1125	0.0003	1.0000

GU-071

0	1	0.24	0.3591	0.5135	0.1055	0.0002	1.0000
---	---	------	--------	--------	--------	--------	--------

0	1	0.25	0.3591	0.5216	0.0988	0.0001	1.0000
---	---	------	--------	--------	--------	--------	--------

null	ntox	a	tox	fut	toxend	power	cksum
1	0	0.00	0.0082	0.0821	0.0233	0.8732	1.0000
1	0	0.01	0.0082	0.0892	0.0230	0.8626	1.0000
1	0	0.02	0.0082	0.0967	0.0227	0.8508	1.0000
1	0	0.03	0.0082	0.1047	0.0224	0.8377	1.0000
1	0	0.04	0.0082	0.1130	0.0221	0.8232	1.0000
1	0	0.05	0.0082	0.1218	0.0218	0.8072	1.0000

null	ntox	a	tox	fut	toxend	alpha	cksum
1	1	0.00	0.3591	0.0222	0.5301	0.0886	1.0000
1	1	0.01	0.3591	0.0251	0.5271	0.0887	1.0000
1	1	0.02	0.3591	0.0281	0.5240	0.0888	1.0000
1	1	0.03	0.3591	0.0315	0.5206	0.0887	1.0000
1	1	0.04	0.3591	0.0351	0.5170	0.0887	1.0000
1	1	0.05	0.3591	0.0391	0.5132	0.0885	1.0000
1	1	0.06	0.3591	0.0433	0.5091	0.0882	1.0000
1	1	0.07	0.3591	0.0478	0.5048	0.0878	1.0000
1	1	0.08	0.3591	0.0526	0.5003	0.0874	1.0000
1	1	0.09	0.3591	0.0577	0.4955	0.0867	1.0000
1	1	0.10	0.3591	0.0632	0.4904	0.0859	1.0000
1	1	0.11	0.3591	0.0690	0.4851	0.0849	1.0000
1	1	0.12	0.3591	0.0751	0.4795	0.0838	1.0000

1	1	0.13	0.3591	0.0815	0.4737	0.0824	1.0000
1	1	0.14	0.3591	0.0882	0.4676	0.0807	1.0000
1	1	0.15	0.3591	0.0953	0.4612	0.0789	1.0000
1	1	0.16	0.3591	0.1027	0.4546	0.0767	1.0000
1	1	0.17	0.3591	0.1105	0.4478	0.0743	1.0000
1	1	0.18	0.3591	0.1185	0.4407	0.0716	1.0000
1	1	0.19	0.3591	0.1268	0.4333	0.0686	1.0000
1	1	0.20	0.3591	0.1355	0.4257	0.0654	1.0000
1	1	0.21	0.3591	0.1445	0.4179	0.0620	1.0000
1	1	0.22	0.3591	0.1537	0.4098	0.0583	1.0000
1	1	0.23	0.3591	0.1632	0.4016	0.0545	1.0000
1	1	0.24	0.3591	0.1730	0.3931	0.0505	1.0000
1	1	0.25	0.3591	0.1830	0.3845	0.0465	1.0000

(Source document for sample collection times/comments – PSLmaster signature sheet in CTO)

IRB 14-052

GU-071: Phase I/II study of ixazomib with pegylated IFN-alpha 2b (pIFN) in metastatic renal cell carcinoma (mRCC)

Ixazomib is an orally administered proteasome inhibitor and can neutralize NF-κB pro-survival signaling preventing the induction of antioxidant enzymes in the cell. IFN induces reactive oxygen species accumulation to toxic levels when NF-κB is disabled and this can lead to mitochondrial dysfunction and necrotic death. IFN-α2b is administered by subcutaneous injection weekly for 8 weeks. Ixazomib is orally administered weeks 2, 3, 4, 6, 7, 8. **A cycle is 28-days.**

Phase I – dose escalation of both ixazomib and IFN-α2b .

Phase II – expansion of the recommended combination doses.

PBMC – Used to examine STAT1 phosphorylation and MHC class I up-regulation (*indicator of IFN activity*) by flow cytometry and pSTAT1 by western blot. [name] lab will perform Western. PSL will stain flow tubes and take to Clin. Path. to acquire. [name] will provide antibodies and analyze flow. *Follow PBMC procedure.*

IL-6 sera levels – Clot and spin at 2000 x g 15min., aliquot and freeze at -70°C. At the end of the study [name] lab will purchase IL-6 kit . PSL, in conjunction with [name] lab, will perform ELISA.

Archival tissue – Look for activated tissue stroma (desmoplasia); IHC for NF-κB p65 and phoso-STAT1.

Pathology will be reviewed By [name] and she select an appropriate block to cut.

If a biopsy or additional surgery is performed during treatment, unstained slides will be prepared on the “on-treatment/EOT tissue”, if patient has consented.

Sample name	#	Volume (mL) gtt procedure:	Time	Volume (mL) aliquots	Time	Final tissue
						1) unstained sections on slides 2) pathology report 3) optional tissue 4) No _____
		CRU				
1 Day 1 Pre 0hr	1, 2, 3, 4					
Day 8 Pre 0hr	2					
Day 15 Pre 0hr	3					
2 Day 1 Pre 0hr	5, 6, 7, 8					
Day 15 Pre 0hr	7					
3 Day 1 Pre 0hr	9, 10, 11, 12					
4 Day 1 Pre 0hr	13, 14, 15, 16					
6 Day 1 Pre 0hr	25, 26, 27, 28					
8 Day 1 Pre 0hr	33, 34, 35, 36					
10 Day 1 Pre 0hr	41, 42, 43, 44					
12 Day 1 Pre 0hr	49, 50, 51, 52					
14 Day 1 Pre 0hr	56, 57, 58, 59					
16 Day 1 Pre 0hr	64, 65, 66, 67					
End of Study						atment/EOT Optional

IRB 14-052

GU-071: Phase I/II study of ixazomib with pegylated IFN-alpha 2b (pIFN) in metastatic renal cell carcinoma (mRCC)

Patient name _____ Study # _____

Mr# _____ Date _____

Cycle 1 Day 1(week 1) Baseline _____ Cycle 1 Day 8(week 2) _____ Cycle 1 Day 15(week 3) _____ Cycle 2 Day 15(week 7) _____
gtt _____ mL blood

PBMC Procedure:

1. Dilute blood 1:1 with PBS (1-50mL conical) and layer over 15mL Ficoll-Paque (1-50mL conical).
2. Centrifuge 500 x g (1500rpm) 30min room temperature - Brake off.
3. Collect PBMC into clean 50mL conical, fill with PBS and spin 2000rpm 5min.
4. Remove and discard supernatant; lyse rbc's with equal amounts (5-10mL) 0.2% NaCl followed by 1.6% NaCl.
5. Remove a portion of cells to count, determine viability with Trypan blue exclusion, then spin at 2000rpm 5min.
6. Remove supernatant and discard, resuspend pellet in PBS to 2×10^6 cells/mL.
7. Place 0.5mL of the 2×10^6 cells/mL suspension into each of three labeled flow tubes – pSTAT1, MHC class I and isotype control.
8. Respin remaining suspended cells, remove supernatant, resuspend pellet in 500 μ L PBS and transfer to 2mL microfuge tube, rinse original tube with 500 μ L PBS and add to microfuge tube.
9. Spin microfuge tube at 2000rpm in microfuge, pour-off and blot tube dry on paper towel, then freeze pellet on dry ice and place at -70°C for storage.

Count cells #/25 squares _____

Volume _____

Total cells _____ ($2 \times 10,000 \times \# \text{cells}/25 \text{ squares} \times \text{volume} = \text{total cells}$) $/2 \times 10^6 =$ _____ mL to resuspend cells

cells/flow tube _____ # tubes _____

cells in frozen pellet _____ (minimum 3×10^6 cells in pellet)

TEMPLE HEALTH

